To avoid type II error, sample size calculation is performed using G*POWER statistical software (version 3.1.9.2; Franz Faul, Universitat Kiel, Germany). To detect a large effect size of 0.4 with power of 80% and $\alpha=0.05$, the required sample size required for this study was $N=66$.

Ethical consideration:

- Approval of faculty ethical committee.
- The study procedure will be explained for all participants.
- Confidentiality will be assured.
- An informed consent will be taken from each subject prior to participation.

(Appendix I)

Criteria for the patient selection:

Inclusion criteria:

- 1) Patients will be selected with age range of 20 to 45 years of both genders.
- 2) Body mass index (BMI) will range from 30 to 34.9 kg\m².
- 3) Having more than one symptom for ROME IV for IBS diagnostic criteria **(Appendix II).**
- 4) Prediabetic with glycated hemoglobin HbA1c of 5.7 – 6.4.
- 5) Sedentary subjects with daily steps count less than five thousand steps measured by pedometer **(Prince et al.,2020).**

Exclusion criteria:

Patients with the following criteria will be excluded from the study:

- 1) Communication disorders
- 2) Gasterointestinal bleeding
- 3) Antibiotics or probiotics in the last 2 months
- 4) Recent surgeries in the last 6 months
- 5) Colorectal cancer or any terminal diseases
- 6) Fibromylgia or Multiple sclerosis
- 7) Palpable abdominal mass
- 8) Cardiovascular diseases

- 9) Active smokers
- 10) Musculoskeletal injuries that interfere with exercise program
- 11) Upper respiratory infections
- 12) Uncontrolled hypertension

Patients will be divided into 3 groups:

- **Group (A):** This group will include 22 patients with IBS. These patients will receive 40 minutes of MICT on the treadmill: 5 minutes of warm-up followed by 30 minutes of 65-75% of target heart rate ending with a 5 min cool-down period for 12 weeks along with following low FODMAP diet plan.
- **Group (B):** This group will include 22 patients with IBS. These patients will receive HIIT sessions consisting of a 30 minutes treadmill session a 5 minutes warm-up followed by 10 bouts of 1 minute at 90% of target heart rate interspersed by 10 bouts of 1 min of active recovery at 50% of target heart rate (totaling 20 min), and a 5 minutes cool-down period for 12 weeks along with following low FODMAP diet plan.
- **Group (C)** This group will include 22 patients with IBS. These patients will follow low FODMAP diet plan for 12 weeks

Materials and Methods

- **Evaluation**

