Out comes to be measured:

1) Primary outcomes

- a- Short chain fatty acids via gas chromatography
- b- Glucagon like peptide 1 via Elisa kit

2) Secondary outcomes

- a- Irritable bowel syndrome scoring system

- b- Irritable bowel syndrome quality of life questionnaire (IBS QoL)
- c- Change in body weight via body mass index (BMI)

Evaluation equipment and tools:

a) Gas chromatography: SCFAs butyrate and acetate

For SCFA analyses, fecal sample will be separated. Applying four analytes, including total SCFAs, acetate, propionate, and butyrate, will be targeted. Final concentrations will be calculated based on internal standards and are expressed as micromoles per gram of wet feces ($\mu\text{mol/g}$). Techniques and predictive approaches will be used across. gas chromatography will be used to quantify Short Chain Fatty Acids (SCFAs) from fecal samples (**Chen et al.,2021**).

b) Elisa Kit for serum GLP 1 hormone

This kit is an Enzyme-Linked Immunosorbent Assay (ELISA). The plate will be pre-coated with Human GLP-1 antibody (**Kuhre et al.,2015**).

c) Weight and Height measurements

Weight and height will be recorded to calculate body mass index (BMI) according to the following equation: (**Shukohifar et al.,2022**)

$$\text{BMI} = \text{weight}/\text{height}^2 \text{ (Kg/m}^2\text{)}.$$

d) IBS severity scoring system (Appendix III)

This five-item questionnaire will measure IBS symptom severity by addressing abdominal pain (frequency and severity), bloating, dissatisfaction with bowel habits, and interference with daily activities. Each question score ranges from 0 to 100 and a higher score indicates more severe GI symptoms. A total score of 75–175 represents mild IBS, 176–300 moderate IBS and >300 severe IBS (**Zeid et al.,2020**).

e) Irritable bowel syndrome quality of life questionnaire (IBS QoL) (Appendix IV)

The IBS-QoL is a condition-specific instrument will be used to assess the impact of IBS and effects of treatment. It consists of 34 questions which cover eight domains including dysphoria, interference with activity, body image, health worry, food avoidance, social reaction, sexual, and relationships. Each item has a five-point response scale (not at all, slightly, moderately, quite a bit, extremely). The responses are summed and averaged for a total score and transformed to a scale between 0 and 100: higher scores indicating better IBS-specific QoL (Hou et al.,2015).

3-Management procedure:

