Appendix III

IBS Severity Scoring System

IBS Severity Score

Place an X anywhere on the line between 0 and 100 to indicate as accurately as possible the severity of your symptoms.

How severe is your pain?

If currently in pain, how severe is your abdominal pain?

If you currently have abdominal distention, how severe is it?

How satisfied are you with your bowel habits?

How much does your IBS affect or interfere with your life in general?

NOTE: Each of the five questions generates a score from 0 to 100 points, with a maximum total score of 500 points. Mild IBS = 75 to 174 points; moderate IBS = 175 to 299 points; and severe IBS = 300 points or more.

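### The protocol describes an IBS severity score that includes pain frequency, but the form it cites asks about pain severity twice and pain frequency never

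*Combined protocol and SAP*

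**What the plan says.** Under Evaluation equipment and tools, item d), the protocol describes a five-item questionnaire for symptom severity, "addressing abdominal pain (frequency and severity), bloating, dissatisfaction with bowel habits, and interference with daily activities". Each item runs from 0 to 100 and higher means worse. The heading of that item, "IBS severity scoring system (Appendix III"), points to the form that patients will complete.

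Appendix III prints five questions. In the order printed, they are:

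1. "How severe is your pain"
2. "If currently in pain, how severe is your abdominal pain"
3. "If you currently have abdominal distention, how severe is it"
4. a question on satisfaction with bowel habits
5. "How much does your IBS affect or interfere with your life in general"

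The note beneath them reads: "Each of the five questions generates a score from 0 to 100 points, with a maximum total score of 500 points".

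The score is listed among the secondary outcomes. The statistical section plans means, standard deviations and Pearson correlations for the measured variables, and does not mention the severity bands.

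**The concern.** The description and the form cannot both be right about what the total contains. A score with separate frequency and severity items responds directly when pain comes less often, even if each episode is as bad as before. A score with two severity items and no frequency item has no direct response to that change.

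If the form is used as printed, a report that follows the protocol's description would tell readers that pain frequency was measured when it was not. It would also attach the name and cut-points of one score to a different mix of items. A question that was never asked cannot be recovered after data collection, so the mismatch has to be settled before the form is used.

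**Working it through.** **Reproducing the stated maximum.** Appendix III gives five questions of 0 to 100, so 5 × 100 = 500, which matches its note. The description in the Evaluation section also implies 5 × 100 = 500. Because the two totals agree, the maximum alone does not reveal the mismatch.

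**Matching items to the description.**

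| Construct in the Evaluation section | Implied points | Appendix III question | Points on the form |
|---|---|---|---|
| Pain frequency | 100 | none | 0 |
| Pain severity | 100 | items 1 and 2 | 200 |
| Bloating | 100 | item 3 | 100 |
| Bowel habits | 100 | item 4 | 100 |
| Interference | 100 | item 5 | 100 |
| Total | 500 | five questions | 500 |

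- Pain severity: 200/500 = 40% on the form, against 100/500 = 20% in the description.
- Pain frequency: 0/500 = 0% on the form, against 100/500 = 20% in the description.

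**Could a question have been lost in reading the PDF?** No. The note counts five questions and five are legible. Response lines and their end labels do not appear in the text as read, but a missing label would not turn a severity question into a frequency question.

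**Is pain frequency measured elsewhere?** None of the 34 questions in Appendix IV (IBS-QoL) mentions pain. Across the two questionnaires, the number of pain-frequency questions is 0 of 5 + 34 = 39. The inclusion criterion "Having more than one symptom for ROME IV for IBS diagnostic criteria" refers to the Rome IV criteria in Appendix II, which require pain on at least 1 day per week on average. That is a threshold at entry and not an outcome.

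**Indirect sensitivity.** Items 1 and 5 may move if pain becomes less frequent. Item 2 may too. If it is scored 0 when the patient is not in pain, its group mean is p × s, where p is the share of patients in pain when they complete the form and s is the mean severity among those patients. A fall in p lowers the mean even if s is unchanged. The form is therefore less directly sensitive to pain frequency, but not blind to it.

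**Cut-points.** The Evaluation section has mild 75–175, moderate 176–300 and severe above 300. Appendix III has mild 75–174, moderate 175–299 and severe from 300. For whole-number totals these differ at two values only: 175 (mild against moderate) and 300 (moderate against severe).

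**The case against.** The best defence is that this is one secondary outcome, given identically to all three groups, and that the research question and hypothesis name only gut dysbiosis and glucagon-like peptide. That stands, and it is why the point is minor. It is also fair that item 2 is not a pure duplicate of item 1, since it picks up whether pain is present at the time of completion. But this is not the separate frequency item that the protocol says it has.

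A reader might infer something stronger from items 2 and 3, which are conditional on a current symptom and together carry 200 of 500 points: that the total is undefined for a patient who is free of pain or distention, so that scoring could diverge widely. For example, if both symptoms are absent and the other three items are assumed to average 40, the total is 3 × 40 = 120 with zeros and 5 × 40 = 200 if prorated. The documents do not support that reading. The form uses a 0 to 100 severity line and its note says that every question generates a score, which points to 0 for an absent symptom. Prorating appears nowhere in the plan. Labels that settle the matter may have been lost from the text as read. An explicit sentence would help, but this is a clarification and not a demonstrated defect.

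A reader might also infer bias between groups. None is shown, because the form is the same in every group.

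**Conclusion.** The inconsistency is established from the text alone: the cited form does not contain the pain-frequency item that the protocol describes. Its size is a shift of 100 of the 500 points (20% of the total) from pain frequency to pain severity. The weights assume that each construct named in the Evaluation section stands for one 0–100 item, which fits its count of five items.

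The point is minor. It affects how one secondary outcome is defined and interpreted. The primary outcomes do not use this score, and the sample-size statement does not depend on its content, so N = 66 stands. The documents give no basis for saying which of the two descriptions was intended.

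**What to change.** Reconcile item d) of the Evaluation section with Appendix III before the form is used, in one of two ways:

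- Use a version of the form that contains the pain-frequency item the Evaluation section describes, and confirm that the severity cut-points apply to that version.
- If the Appendix III form is the intended one, correct the Evaluation section to say that pain frequency is not measured.

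Make three small clarifications in the same edit, after checking the source form for labels that may not have survived the PDF reading:

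- State that an absent symptom on a conditional item is scored 0.
- Confirm that item 4, which asks about satisfaction, is scored so that higher means worse, as the Evaluation section requires.
- Keep one set of severity cut-points.

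The cost is a replaced form or one corrected sentence, plus a few scoring lines. It needs no extra visits, staff or patients.

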Moderate aerobic exercise affects the intestinal system mainly through gut immune function, gut barrier integrity, as well as gut motility, intestinal pH and gut hormones release; and bile acids metabolism within enterohepatic circulation (**Resende et al., 2021**).

Also High-intensity interval training is a popular, time-efficient mode of exercise to improve metabolic health and aerobic fitness, both of which have been associated with healthier gut bacterial community structure (**Rettedal et al., 2020**).

Statement of the Problem:

Is there a significant difference between the effect of moderate continuous versus high interval intensity training on gut dysbiosis and glucagon like peptide hormone in irritable bowel syndrome?

The Purpose of the Study:

To compare the effect of moderate continuous versus high interval intensity training on gut dysbiosis and glucagon like peptide hormone in irritable bowel syndrome.

Significance of the Study:

Irritable bowel syndrome affects around 11% of the global population with variation by geographic region: the highest in South America (21.0%) and the lowest occurring in South Asia (7.0%). In Egypt, the prevalence was 34% in primary healthcare center attendees. IBS significantly reduces work productivity and health-related quality of life (**Mohamed et al.,2021**).

The quality of life for patients suffering from IBS is greatly affected physically, psychologically, and economically. Several cases reported difficulties in concentration, decreased energy level, and lower self-esteem. In-addition IBS is

inducing occupational hazards as it affects the performance of patients at their jobs (**Elsayed et al.,2021**).

Although half of the cases referred to gastroenterologists is due to IBS, no clear etiology was found; however, some researches revealed that certain factors such as psychological factors, dietary habits, and exercise level were related to IBS onset and course (**Elhosseiny et al.,2019**).

Previous studies have been done separately on the effect of moderate intensity continuous training program and high intensity interval training on irritable bowel syndrome and gut dysbiosis, it is rational to compare between two training programs to know which is more effective to improve gut microbiota balance.

Delimitations:

This study will be delimited to the following aspects:

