Subjects will be delimited to patients with irritable bowel syndrome selected from the outpatient of national nutrition institute with the following criteria:

- Sixty six patients with irritable bowel syndrome of both genders.
- Their ages ranged from 20 to 45 years.
- Their Body mass index ranged from 30 to 34.9.
- Patients will be divided into 3 groups
 - **Group A:** Patients will receive moderate intensity continues training exercise program along with following Low fermentable, oligosaccharides, disaccharides, monosaccharides and polysaccharides diet plan (FODMAPs diet).
 - **Group B:** Patient will receive high intensity interval training exercise program along with following FODMAP diet plan.

- **Group C:** Patients will follow FODMAP diet plan only.
- Patients will be excluded if:
 - - Uncontrolled hypertension
 - - Gastrointestinal bleeding
 - - Colorectal cancer or any terminal diseases
 - - Communication disorders

Basic Assumptions:

It will be assumed that:

- 1) The primary medical assessment will be done to every participating patient who includes:
- 2) Complete medical history (personal, present and past)
- 3) All patients will stick to the program and will follow instructions.
- 4) All other factors which may influence the outcome such as noise and distraction will be controlled.

Hypothesis:

It will be hypothesized that there will be no significant difference between the moderate continuous versus high interval intensity training on gut dysbiosis and glucagon like peptide hormone in irritable bowel syndrome.

CHAPTER II

REVIEW OF LITERATURE

The human gastrointestinal (GI) tract represents one of the largest organ between the host, environmental factors and antigens in the human body. In an average life time, around 60 tonnes of food pass through the human GI tract, along with an abundance of microorganisms from the environment which impose a huge threat on gut integrity. The collection of bacteria, archaea and eukarya colonising the GI tract is termed the ‘gut microbiota’ and has co-evolved with the host over thousands of years to form an intricate and mutually beneficial relationship (**Thursby and Juge,2017**).

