Among humans, positive correlations were reported between bacterial diversity, butyrate-producing bacteria and cardiorespiratory fitness (VO₂max), and higher turnover of carbohydrates and proteins, and concentrations of short-chain fatty acids in athletes compared to sedentary controls. There is also growing evidence that physical activity status and exercise training may shape the gut microbiome (**Cataldi et al.,2022**).

Physical activity stimulates bacterial community richness by altering SCFAs-producing species, as well as favoring the colonization of health and athletic performance-promoting strains. The ability to promote a bacterial

composition capable of protecting the intestinal mucosa also it was found that the effects on gut microbiome seem to gradually disappear when the physical activity is no longer practiced (**Cataldi et al., 2022**).

Moderate aerobic exercise affects the intestinal system mainly through gut immune function gut barrier integrity through tight junction proteins expression and IgA production hypothalamic–pituitary–adrenal (HPA) axis stimulation which, in turn, affects enteric nervous system and intestinal transit time, as well as gut motility, intestinal pH and gut hormones release and bile acids metabolism within enterohepatic circulation (**Cella et al.,2021**).

High intensity interval training (HIIT) encompasses exercise prescriptions that are tailored to individual needs and can be used in most any exercise setting. This ability to adapt makes HIIT a valuable tool in the exercise programming of patients with a chronic disease. HIIT has a positive effect on the Bacteroidetes/Firmicutes ratio and also increased the alpha diversity in gut microbiota (**Denou et al.,2016**).

Chapter III

[figure not shown]
PATIENTS, MATERIALS AND METHODS

The current study is designed to compare between the effect of moderate continuous and high interval intensity training on gut dysbiosis and glucagon like peptide hormone in irritable bowel syndrome.

I. Patients:

This study will be carried out on sixty six irritable bowel syndrome patients of both sexes with an age range between twenty to forty five years. Patients will be recruited and practical work of the study will be carried out in national nutrition institute physiotherapy out clinic. Patient will be randomly assigned to three groups.

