After collecting the consent forms, will be examined by the researcher for the inclusion and exclusion criteria. Each eligible patient (according to the consent form and examination) will participate in the study.

Group A

Patients will receive moderate intensity continuous training (MICT).

The program will be in form of: (Clark et al.,2020).

- **Frequency:** Moderate continues training will be scheduled 3 times per week for 12 weeks
- **Intensity:** 65-75% of target heart rate.
- **Duration:** 40 minutes per session. Patients will be instructed to follow low fermentable short chain carbohydrates diet (low FODMAP) intervention for 12 weeks limiting daily fermented carbohydrate and dairy products intake and increase intake of protein, whole grains, fruits and vegetables

(Appendix V)

- **Group B**

Patients will receive high intensity interval training (HIIT)

The program will be in form of: **(Clark et al.,2020).**

- **Frequency:** High intensity interval training will be scheduled 3 times per week for 12 weeks
- **Intensity:** 90% of target heart rate including 10 bouts of 1 minute interspersed with 10 bouts of 1 minute of active recovery 50% of target heart rate.
- **Duration:** the session will last 30 minutes includes warming up and cooling down periods

Patients will be instructed to follow low fermentable short chain carbohydrates diet (low FODMAP) intervention for 12 weeks limiting daily fermented carbohydrate and dairy products and increase intake of protein, whole grains, fruits and vegetables

Group C

Patients will be instructed to follow low fermentable short chain carbohydrates diet (low FODMAP) intervention for 12 weeks limiting daily fermented carbohydrate and dairy products and increase intake of protein, whole grains, fruits and vegetables **(Vareny et al.,2017).**

Only the patients who will attend > 80% of the exercise training sessions will be included in this study.

Data Analysis and statistical design

- The collected data was analyzed using the statistical program SPSS ver. 20.0.
- The mean and standard deviation were calculated for all measured variables.
- Pearson correlation coefficient was used to determine the relationship between the measured variables.
- Statistical significance was set at $p < 0.05$.

REFERENCES

Aziz I & Simrén M (2021). The overlap between irritable bowel syndrome and organic gastrointestinal diseases. *The Lancet Gastroenterology & Hepatology*, 6(2), 139–148.

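### The > 80% attendance rule removes patients after randomisation, can sensibly act only on the two exercise groups, and is the only statement of whose data count

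*Combined protocol and SAP*

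**What the plan says.** Under I. Patients, allocation is random: "Patient will be randomly assigned to three groups". Eligibility is settled at consent and examination, at the start of the Management procedure: "Each eligible patient (according to the consent form and examination) will participate in the study". Groups A and B each train three times a week for 12 weeks (for A, "Moderate continues training will be scheduled 3 times per week for 12 weeks"). Group C does no training: "These patients will follow low FODMAP diet plan for 12 weeks".

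After the Group C text, the Management procedure ends with: "Only the patients who will attend > 80% of the exercise training sessions will be included in this study". This condition is not in the inclusion or exclusion lists. Nothing comparable, such as a diet-adherence threshold, is set for Group C.

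The section Data Analysis and statistical design covers only software, means and standard deviations, Pearson correlation and the significance level. It names no analysis set, missing-outcome method or between-group test. Basic Assumptions includes: "All patients will stick to the program and will follow instructions". The sample size text says "the required sample size required for this study was" N = 66, which is 22 per group, without saying whether these are randomised or evaluable patients.

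**The concern.** A rule based on attendance cannot be an entry criterion, because attendance is observed only after assignment. Used to decide who is counted, it replaces the randomised groups with groups selected by behaviour during treatment.

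- **A-C and B-C.** Selected patients are compared with unselected ones. If people who attend regularly would have done better or worse anyway, the contrast carries that difference as well as any effect of training.
- **A-B.** The threshold is the same in both arms, but the two programmes may lose different numbers or different kinds of patient. Equal exclusion rates alone do not protect this contrast.
- **The question.** If attendance is related to outcome only because more sessions produce more effect, the rule changes the question to the effect in attenders. Significance of the Study gives the aim more broadly: "it is rational to compare between two training programs to know which is more effective".

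No as-randomised result is planned alongside, so a reader could not judge how much the rule had altered the findings. Sampling times for short chain fatty acids and GLP-1 are not stated either, so it is unclear whether poor attenders would be measured at all.

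**Working it through.** **The threshold.** 3 sessions x 12 weeks = 36 sessions, and 0.8 x 36 = 28.8. Since 28/36 = 77.8% fails and 29/36 = 80.6% passes, the rule means at least 29 sessions in A and B. Group C has none.

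**The plan's own figure.** Inputs from the sample size text are effect size 0.4, power 80% and alpha 0.05, with three groups. I take 0.4 as Cohen's f and the test as a one-way F test; both are inferred. Power is P(F' > F crit), where F' is noncentral F on 2 and N - 3 degrees of freedom with lambda = N x f².

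- N = 66: lambda = 66 x 0.16 = 10.56, power 0.818
- N = 63: lambda = 63 x 0.16 = 10.08, power 0.798

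So 66 is the smallest balanced total that reaches 80%, and it contains no allowance for exclusions.

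**Power if 66 are randomised and only A and B lose patients.** Here lambda is the sum of n_i x (mu_i - weighted mean)². The means are scaled to f = 0.4 over six patterns: each group in turn differing from the other two, and each in turn midway between them.

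| A/B/C analysed | Loss in A and B | Power |
|---|---|---|
| 20/20/22 | 2/22 = 9.1% | 0.777 to 0.803 |
| 18/18/22 | 4/22 = 18.2% | 0.728 to 0.785 |
| 17/17/22 | 5/22 = 22.7% | 0.700 to 0.775 |

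If 66 means evaluable patients, there is no power loss, but the selection problem remains.

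**Selection bias, A-C (illustration).** Assume no true effect, and attendance propensity correlated rho with outcome. The lowest fraction q of A and B is excluded and none of C. The retained mean shifts by rho x phi(z_q)/(1 - q) standard deviations. At q = 0.20, z = -0.842, phi = 0.280 and 0.280/0.80 = 0.350, so rho = 0.5 gives 0.175. Rejection rates are for the three-group F test at 5%, from 40,000 simulated trials with 22 randomised per arm.

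| q in A and B | rho | Shift (SD) | F test rejects |
|---|---|---|---|
| 5% | 0.3 | 0.033 | 5.1% |
| 10% | 0.3 | 0.058 | 5.3% |
| 10% | 0.5 | 0.097 | 5.9% |
| 20% | 0.3 | 0.105 | 6.1% |
| 20% | 0.5 | 0.175 | 8.3% |
| 30% | 0.3 | 0.149 | 6.8% |
| 30% | 0.5 | 0.248 | 11.1% |

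With rho = 0 the rate is 4.7% to 5.0%.

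**Selection bias, A-B (same assumptions, two-sample t test).**

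| q in the two arms | rho in the two arms | Shift (SD) | t test rejects |
|---|---|---|---|
| 20%/20% | 0.3/0.3 or 0.5/0.5 | 0 | 4.8% or 5.0% |
| 20%/20% | 0.3/0.1 | 0.068 | 5.3% |
| 20%/20% | 0.5/0.1 | 0.141 | 6.8% |
| 20%/20% | 0.5/0 | 0.174 | 8.1% |
| 15%/35% | 0.3/0.3 | 0.090 | 5.8% |
| 15%/35% | 0.5/0.5 | 0.148 | 7.0% |

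The first row is the case in which the rule does no harm to A-B.

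**The case against.** The strongest counter-case is that the trial's question is A against B, as the Statement of the Problem and the Hypothesis put it. For that contrast the rule is symmetric: 36 sessions and the same threshold in each arm. The documents give no evidence that exclusion, or its relation to outcome, differs between the programmes. If both are alike, the illustration shows no shift and about 5% error. This stands as a limit on the A-B part, which is conditional. It does not help A-C and B-C, where the asymmetry is built in, and the plan contains nothing that would show whether the A-B condition was met.

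Three further points are fair.

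- **Reading of the rule.** Taken literally, it would remove all of Group C, who attend no sessions. That it filters A and B only is the workable reading. The sentence also speaks of inclusion in the study, not of an analysis set; that it decides whose data count is an inference from there being no other text on the matter.
- **Tension, not contradiction.** An assumption of adherence can coexist with a rule for non-adherence, and the statement that eligible patients participate concerns enrolment. Both sit uneasily with the rule, but the point does not depend on them.
- **Interest in adherers.** The aim does not explicitly specify the effect as assigned, and the effect under adherence is a legitimate interest. However, simply dropping poor attenders from two arms and nobody from the third does not validly estimate that effect either.

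**Conclusion.** The concern holds. As written, the plan applies a post-randomisation exclusion that can work only in the exercise groups, with no as-randomised analysis to set against it. A-C and B-C are open to selection bias if attendance is prognostic. A-B is open to it if the exclusion rate or the attendance-outcome relation differs between the programmes.

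The size cannot be determined from the documents. It could be negligible if few patients are excluded and the correlation is modest, or reach about a quarter of a standard deviation for A-C at 30% exclusion and correlation 0.5. All exclusion rates and correlations are assumed. The case for correction rests on the design logic, not on these figures. The power loss applies only if 66 is the number randomised; two exclusions from each exercise arm can then already bring power below 80%.

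**What to change.** Replace the attendance sentence with text to this effect:

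> All randomised patients will be assessed at the end of the 12-week programme regardless of attendance and analysed in the group to which they were randomised (primary analysis). An analysis restricted, in Groups A and B, to patients who attended more than 80% of sessions will be a labelled supplementary analysis. The number at or below 80% and the number without outcome data will be reported by group.

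The supplementary analysis should carry a note that its contrasts with Group C remain asymmetric. For the primary analysis to work, the plan also needs:

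- baseline and end-of-programme sampling times;
- one pre-specified method for missing outcomes (multiple imputation is one option);
- a statement of whether 66 is randomised or evaluable, with power restated for expected losses if it is randomised;
- wording under Basic Assumptions that is reconciled with the new text.

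**Cost.** The change needs revised wording and outcome samples from poor attenders, and does not in itself require more recruitment. If collection has closed, analyse every patient with an outcome sample as randomised and report exclusions by group.

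The real price is dilution. Suppose 20% are poor attenders who receive half or none of the effect (assumed). The as-randomised effect is then 0.8 + 0.2 x 0.5 = 0.90, or 0.8 + 0.2 x 0 = 0.80, of that in attenders. If f = 0.4 described attenders and every contrast shrank in that proportion, f would be 0.36 or 0.32. Lambda would be 66 x 0.36² = 8.55 or 66 x 0.32² = 6.76, and power at N = 66 would be 0.73 or 0.62. Restoring 80% in that case would need more patients, so the sample size should be reconsidered if such dilution is expected.

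### The >80% attendance rule excludes patients after randomisation and can work only in Groups A and B, so comparisons with C, and possibly MICT versus HIIT, are open to selection bias of unknown size

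*Combined protocol and SAP*

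**What the plan says.** All references are to the combined protocol and SAP.

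- **Allocation** (Chapter III, I. Patients): "Patient will be randomly assigned to three groups". The group descriptions give 22 patients to each of A, B and C, 66 in all.
- **Sessions** (Management procedure): for Group B, "High intensity interval training will be scheduled 3 times per week for 12 weeks". Group A has the same frequency. Group C receives the diet only.
- **Attendance rule** (last sentence of the Management procedure section): "Only the patients who will attend > 80% of the exercise training sessions will be included in this study".
- **Adherence** (Basic Assumptions, item 3): "All patients will stick to the program and will follow instructions". No diet-adherence rule is set for Group C, and no allowance for dropout is given.
- **Sample size**: "To detect a large effect size of 0.4 with power of 80"% and a two-decimal alpha of 0.05, giving 66. The test is not named.
- **Analysis** (Data Analysis and statistical design): "The mean and standard deviation were calculated for all measured variables". The section adds Pearson correlation and a significance level. It names no analysis population, no between-group test and no method for missing outcomes.

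**The concern.** Randomisation makes the groups comparable as they were assigned. A rule that removes patients by how they behaved after assignment can undo that. Patients who miss many sessions may differ from the others in motivation, symptoms, fitness or diet adherence. If those traits relate to the outcomes, taking such patients out of A and B while their counterparts stay in C can create a difference or hide one.

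The stated research question is MICT versus HIIT. Those two arms face the same rule and the same number of sessions, so similar losses would largely cancel. If one programme loses more patients, or a different kind of patient, that comparison also loses its protection.

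The choice has to be made before conduct. If removed patients are not followed, their 12-week outcomes cannot be recovered at analysis.

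**Working it through.** **1. The plan's sample size.** Read 0.4 as Cohen's f in a one-way ANOVA with three groups, alpha 0.05, noncentrality f² × N = 0.16 × 66 = 10.56. Power is 0.818. The next smaller balanced total, 63, gives 0.798. So 66 is reproduced, with no margin for removals.

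**2. The threshold.** 3 × 12 = 36 sessions, and 0.80 × 36 = 28.8.
- 29/36 = 80.6% passes.
- 28/36 = 77.8% fails.
- A patient is removed at 36 − 28 = 8 missed sessions, about 8/3 = 2.7 weeks of training.

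**3. Shift in an arm's mean.** Remove k of 22, and let d be the retained mean minus the removed mean, in SD units. The retained mean differs from the full-arm mean by (k/22) × d. The values of k and d are assumptions; the documents give neither.

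| k | share removed | shift, d = 0.5 | shift, d = 1.0 |
|---|---|---|---|
| 1 | 4.5% | 0.023 SD | 0.045 SD |
| 2 | 9.1% | 0.045 SD | 0.091 SD |
| 4 | 18.2% | 0.091 SD | 0.182 SD |

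For scale, suppose A and B differ equally from C by m. Then f = m × √2/3, so m = 0.4 × 3/√2 = 0.849 SD. The shifts are 0.023/0.849 = 3% to 0.182/0.849 = 21% of that.

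**4. One exercise arm versus C, no true effect.** Two-sided 5% t test, 22 − k versus 22 patients, noncentrality = shift / √(1/(22 − k) + 1/22), equal variances assumed.

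| k | rejection rate, d = 0.5 | rejection rate, d = 1.0 |
|---|---|---|
| 1 | 5.1% | 5.2% |
| 2 | 5.2% | 6.0% |
| 4 | 5.9% | 8.6% |

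**5. A versus B, no true effect.** Take 2 removed in one arm and 4 in the other, d = 1.0. The difference in shifts is 0.182 − 0.091 = 0.091 SD, with 20 versus 18 patients. Noncentrality is 0.091/√(1/20 + 1/18) = 0.28 on 36 degrees of freedom, and the rejection rate is about 5.9%. With equal numbers removed and the same d in both arms, the shifts cancel and the rate is 5.0%.

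**6. Power cost of analysing everyone.** One-way ANOVA, A and B each 0.849 SD better than C, k removed from each exercise arm. In the extreme case low attenders get no exercise benefit, so the effect with all patients included is multiplied by (22 − k)/22. The fair comparator is the present rule with the same removals.

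| k per exercise arm | present rule | all 66 as assigned |
|---|---|---|
| 1 | 21/21/22: 81% | effect × 21/22 = 95%: 78% |
| 4 | 18/18/22: 79% | effect × 18/22 = 82%: 64% |

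**The case against.** **The main question is A versus B, and the rule treats A and B alike.** This stands in part. Bias there needs unequal removals, and the illustrated excess is under one percentage point. It limits the size of the point but does not remove it: nothing in the plan ensures equal losses, and a three-group design invites comparison with C.

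**The figures are assumed.** This stands. The documents give no attendance data and no link between attendance and stool SCFAs or GLP-1, and they name no between-group test. Most of the grid is close to 5%. The 8.6% corner also ignores the wider spread in C, which keeps its would-be low attenders; a simulation allowing for that gives 8.1%.

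**The sentence could be read otherwise.** It might mean recruiting until 22 attenders are reached in each exercise arm. Selection would remain, but the reduced group sizes used above would not apply. Read literally, the sentence would also exclude all of Group C, which has no sessions; the three-group design makes that unworkable.

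**Stronger readings that a reader might infer.**
- That low attenders will not be followed up. The text does not say so; it says only who is included.
- That safety goes unmonitored because the listed outcomes contain no adverse-event item. That is a separate matter. It cannot be judged fully with the opening and consent pages removed, and it carries no weight here.

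**Conclusion.** The point holds as a design weakness. The rule acts after randomisation, can be applied only to A and B, and no other visible text requires analysis as assigned. Comparisons of A or B with C are open to selection bias. MICT versus HIIT is open to it only if removals differ between those arms in number or type.

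The documents do not show that bias will occur or that it would be large. On the assumptions in the working, the effect on type I error is trivial with one removal and matters only towards four removals with a 1.0 SD gap. The case for change rests on how little it costs to avoid the exposure, not on a demonstrated distortion.

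**What to change.** Replace the attendance sentence in the Management procedure section with:

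> All randomised patients are followed to 12 weeks and analysed in the group to which they were assigned, whatever their attendance; the reason for stopping is recorded; an analysis of A and B patients attending >80% of sessions is secondary.

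Report by arm how many patients have no final outcome. Analysis as assigned does not by itself deal with outcomes that are missing, so this count is needed to judge how far it was achieved.

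**Cost.** A change of wording, a reason column in the attendance log, and the effort of contacting low attenders for their final assessment. With an assumed 1 to 4 per exercise arm, that is 2 to 8 patients, whose samples fall within the 66 final sets already implied by the sample size.

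**Downside.** Dilution, as in step 6. If low attenders get no exercise benefit, power falls from about 81% to 78% with 1 of 22 per exercise arm, or from about 79% to 64% with 4 of 22. The secondary analysis would still describe results in attenders, without the protection of randomisation.
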